6.2 MEASURES TO MINIMIZE BIAS: RANDOMIZATION AND BLINDING

To control for bias, we have decided on a prospective, controlled, triple crossover (three stimulation locations at separate study visits) study design. Participants will be blinded as to stimulation location, and each participant will experience stimulation at all locations. Each participant will have all rating scales performed by the same rater. Potential confounding factors, such as age, disease duration, cognitive function, and overall disease severity will be evaluated and controlled for, as indicated, in the final statistical models.

Stimulation order will be randomized and counter-balanced. Participants are assigned a study ID number and randomized upon signing the informed consent form. Subject ID will be entered into the randomization algorithm by the research assistant. A randomization table will be generated by a computerized script that randomizes and counterbalances by ID, generating an Excel spreadsheet. We will perform complete counterbalancing, there are 6 potential sequences (mPFC-DLPFC-S1, mPFC-S1-DLPFC, DLPFC-mPFC-S1, DLPFC-S1-mPFC, S1-mPFC-DLPFC, S1-DLPFC-mPFC) and a plan for 48 participants. Every effort will be made to completely counterbalance our sample. Thus effects of stimulation order will be minimized.

Treatment Assignment Procedures: Participants will receive stimulation to the medial prefrontal cortex, the dorsolateral prefrontal cortex, and the primary sensory cortex. The order of stimulation will be randomized and counterbalanced. Randomization will be performed using a script that generates a

spreadsheet. Randomization will be done after the screening visit is completed, before initiation of stimulation sessions.

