8.3.3.2 RELATIONSHIP TO STUDY INTERVENTION

All adverse events (AEs) must have their relationship to study intervention assessed by the clinician who examines and evaluates the participant based on temporal relationship and his/her clinical judgment. The degree of certainty about causality will be graded using the categories below. In a clinical trial, the study product must always be suspect.

- **Related** – The AE is known to occur with the study intervention, there is a reasonable possibility that the study intervention caused the AE, or there is a temporal relationship between the study intervention and event. Reasonable possibility means that there is evidence to suggest a causal relationship between the study intervention and the AE.
- **Not Related** – There is not a reasonable possibility that the administration of the study intervention caused the event, there is no temporal relationship between the study intervention and event onset, or an alternate etiology has been established.

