8.3.4 TIME PERIOD AND FREQUENCY FOR EVENT ASSESSMENT AND FOLLOW-UP

The occurrence of an adverse event (AE) or serious adverse event (SAE) may come to the attention of study personnel during study visits, during study telephone calls, and interviews of a study participant presenting for medical care.

All AEs including local and systemic reactions not meeting the criteria for SAEs will be captured on the appropriate case report form (CRF). Information to be collected includes event description, time of onset, clinician's assessment of severity, relationship to study product (assessed only by those with the training and authority to make a diagnosis), and time of resolution/stabilization of the event. All AEs occurring while on study must be documented appropriately regardless of relationship. All AEs will be followed to adequate resolution.

Any medical condition that is present at the time that the participant is screened will be considered as baseline and not reported as an AE. However, if the study participant's condition deteriorates at any time during the study, it will be recorded as an AE.

Changes in the severity of an AE will be documented to allow an assessment of the duration of the event at each level of severity to be performed. AEs characterized as intermittent require documentation of onset and duration of each episode.

Study personnel will record all reportable events with start dates occurring any time after informed consent is obtained until 7 (for non-serious AEs) or 30 days (for SAEs) after the last day of study participation. At each study visit, the investigator will inquire about the occurrence of AE/SAEs since the last visit. Events will be followed for outcome information until resolution or stabilization.

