9.4.4 SAFETY ANALYSES

Safety outcome will be the adverse effects questionnaire filled out at the end of each stimulation session (mean, median, and range), and the presence of AEs, SAEs, and UAEs which are deemed to be related to stimulation. AEs, SAEs, and UAEs reporting will be done at each stimulation visit, as well as 1 day and 4 days after each visit over telephone. Each AE will be counted only once per participant. AEs will be reported as start date, stop date, severity, relationship to stimulation, expectedness, outcome, and duration. Adverse events leading to premature discontinuation from the study, and serious treatment-emergent AEs, will be presented in a table.

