9.4.8 TABULATION OF INDIVIDUAL PARTICIPANT DATA

Individual participant data will not be listed.

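### Sections 8.3.4 and 8.3.5 set conflicting baselines for what counts as an adverse event, and 9.4.4 neither settles the conflict nor states a split by stimulation location

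*Combined protocol and SAP*

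**What the plan says.** **Section 8.3.4** fixes the baseline at screening: "Any medical condition that is present at the time that the participant is screened will be considered as baseline and not reported as an AE". Deterioration at any later time is an AE. Events are recorded if they start after consent and up to 7 days (non-serious) or 30 days (serious) after the last day of participation, whatever their relationship to stimulation. It adds: "At each study visit, the investigator will inquire about the occurrence of AE/SAEs since the last visit".

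**Section 8.3.5** has AEs taken at each stimulation visit and at calls one and four days later. The AE form covers details of the stimulation and whether the event is a worsening of a baseline symptom, and the PI reviews and signs it. The section ends by saying that conditions and symptoms already there before that day's stimulation are not AEs. That resets the baseline at every visit.

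**Section 8.3.3.2** allows an event to be called related where "there is a temporal relationship between the study intervention and event", among other grounds and subject to clinical judgement.

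**Section 9.4.4** names as safety outcomes the adverse effects questionnaire from the end of each session (mean, median and range) and the AEs deemed related to stimulation. On counting, it says: "Each AE will be counted only once per participant". On the attributes to be given, it says: "AEs will be reported as start date, stop date, severity, relationship to stimulation, expectedness, outcome, and duration". On tables, it says: "Adverse events leading to premature discontinuation from the study, and serious treatment-emergent AEs, will be presented in a table". Section 9.4.8 adds: "Individual participant data will not be listed". Under section 6.2, "each participant will experience stimulation at all locations".

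**The concern.** The two AE rules give different answers for the same symptom, and they differ at the moment of recording. A symptom that starts after the day-4 call meets its first scheduled chance of being recorded at the next stimulation visit. That is also the visit at which 8.3.5, taken literally, says it is not an AE. If it never reaches the form, no analysis can bring it back.

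The stated AE outcome in 9.4.4 is events related to stimulation. A symptom that begins after session 1 or 2 could be judged related and so belong in that outcome under 8.3.4, yet be absent from it under 8.3.5. Because treatment-emergent has no definition, 9.4.4 offers no tie-break.

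The secondary matter is reporting. The trial compares three locations within each person, and the efficacy models in 9.4.1 include location, but no location split is stated for any safety summary. The counting sentence in 9.4.4 could also be read as dropping a recurrence that follows stimulation at a different location.

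**Working it through.** There is no stated figure to reproduce. The check is a comparison of texts, with calendar arithmetic.

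**Schedule (section 1.3).** Stimulation visits are at weeks 1, 4 and 7, with calls 1 and 4 days after each.
- Interval between sessions: 3 weeks = 21 days.
- Day-4 call to next session: 21 − 4 = 17 days. There are two such gaps, so 2 × 17 = 34 days.
- First session to last call: 21 + 21 + 4 = 46 days.

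So 34 of 46 days lie between a day-4 call and the next visit. This is calendar time, not a count of events. The days are nominal: section 7.3 allows a missed visit to be rescheduled within two weeks, which would lengthen a gap.

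**The two rules by time of onset.**

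| Onset of a new symptom | 8.3.4 | 8.3.5, read literally |
|---|---|---|
| After screening, still present before session 1 | AE | Not an AE |
| From a session to its day-4 call, reported at a call | AE | AE, recorded at the call |
| After the day-4 call, gone before the next session | AE | Not excluded |
| After the day-4 call, still present before the next session | AE | Not an AE |
| After session 3 | AE, within the recording window | Cannot be excluded, as no session follows |

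The rules part in the first and fourth rows. The first covers up to 7 days by section 1.3, or up to 21 days by section 8.2. Such a symptom cannot have been caused by stimulation, so only the total AE record changes. The fourth row matters more. There a persisting symptom is left out while one that has resolved is kept.

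**Location.** Section 9.4.4 gives seven AE attributes, and location is not among them. It names two AE categories for tabulation and states no columns. The questionnaire is completed after each session and each session has one location, so those scores exist by location, but no split is stated. The AE form and start dates should allow each AE to be matched to a session.

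**The counting sentence.** It follows a list of contacts and precedes event-level dates, so its natural meaning is that one event heard at several contacts is one AE. If it instead meant one count per kind of AE per participant, the effect depends on rates the documents do not give. As an illustration, assume a common probability q at each session, independence between sessions, and 48 participants completing all three:
- Counted once per location: 48 × 3 × q. Counted once per participant: 48 × [1 − (1 − q)³].
- q = 0.05: 7.2 against 6.8, a difference of 0.4.
- q = 0.20: 28.8 against 23.4, a difference of 5.4.
- q = 0.50: 72.0 against 42.0, a difference of 30.0.

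The two readings nearly agree for rare events and diverge for common ones.

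**The case against.** The best defence of 8.3.5 is that its last sentence means only that a symptom already present cannot be counted as a new AE of that day's session. The form's question about worsening of a baseline symptom fits that reading. This may well be the intent, but the sentence denies AE status altogether, so clarification is still needed.

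A reader might infer that staff would code the same symptom inconsistently without check. The documents do not support that: the PI reviews and signs every form and determines relationship (8.3.5), and reviews AEs in real time (10.1.7). What remains is that sign-off cannot recover a symptom that never reached a form.

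A reader might also infer that timing alone makes every such symptom related. Section 8.3.3.2 rests the assessment on timing and clinical judgement together, and an established alternative cause makes an event not related.

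On location, it is tempting to say the plan rules out any safety comparison between targets, or discards recurrences. Neither follows. Section 9.4.4 is silent on table layout, the questionnaire is collected session by session, and the counting sentence has a harmless natural reading. This part is an omission in a pilot study whose objectives do not include safety. It is worth mending because it is cheap.

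**Conclusion.** The AE-baseline conflict stands as written. Sections 8.3.4 and 8.3.5 cannot both be applied to a new symptom that starts after screening, or between a day-4 call and the next session, and is still present at that visit. After stimulation has begun, the conflict mainly concerns two nominal 17-day intervals per participant, and assumes that earlier symptoms are reported at the calls. The missing location split and the unclear counting sentence are secondary: an improvement to make, not an error.

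Severity is minor to moderate. The FMT analyses are unaffected. How many AEs would change status cannot be estimated, because the documents give neither AE rates nor durations. A reader might conclude that the safety results would be materially biased, or worse for one location, but nothing in the documents shows this.

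**What to change.** **Main change.** Reconcile 8.3.4 and 8.3.5 into one AE baseline, and use it to define treatment-emergent in 9.4.4. The choice of rule is the sponsor's. One workable form lets the state before each session decide only whether an event is new to that session, not whether it is an AE. Settle this first: a table can be built later, but an unrecorded symptom cannot be recovered.

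**Secondary change, in 9.4.4.** State that:
- one event reported at several contacts is one AE;
- questionnaire scores are summarised by the location stimulated in that session;
- all AEs, and separately related AEs, are summarised by the location most recently stimulated before onset;
- each kind of AE is counted at most once per participant per location, with participants who started that location's session as denominator, alongside an overall count.

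These are aggregate summaries, so 9.4.8 can stay as it is.

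**Cost.** A few sentences, one more descriptive table, and consistent grouping of AE terms, for which the plan specifies no coding system. No new data collection: onset dates, stimulation details, the calls and the session questionnaire are already planned.

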2.3 RISK/BENEFIT ASSESSMENT

2.3.1 KNOWN POTENTIAL RISKS

Psychological risk

Breach of confidentiality: While there is the potential for breach of confidentiality, all study personnel will minimize this risk to study subjects. All data will be de-identified before analysis, and any treatment outcome data will be treated with strict confidentiality. Electronic data will be stored on password-protected servers within the UNC School of Medicine and any hard-copy data will be stored in locked cabinets in locked offices in the UNC Department of Neurology.

Risk of embarrassment: There is a risk of distress or embarrassment for the participant if they have difficulty performing well on cognitive and physical tests. The research team will take extra care to perform these evaluations in a judgement-free manner, and provide appropriate encouragement to the participant, as is routinely done in a clinical setting. Additionally, we will request that the participant be alone in the examining room with the examiner, without care partner or other persons in the room, while performing these examinations, unless otherwise preferred by the participant, to help minimize this risk.

Physical risk:

Risk of injury and discomfort: Transcranial magnetic stimulation (TMS) is FDA approved for treatment of many neuropsychiatric symptoms in the USA. TMS is not related to electroconvulsive therapy, which applies many orders of magnitude higher stimulation electrical current. The level of electrical stimulation produced by TMS is within the range of activity that is endogenous to the brain. Furthermore, the intensity of stimulation is calibrated to the sensitivity of the individual participant such that the level of stimulation is matched to the naturally occurring brain activity in that individual. In order to monitor side effects, participants will be asked to complete an adverse effects from stimulation questionnaire after each stimulation session. Research personnel supervising the stimulation sessions will also check with the participant periodically during the stimulation session to ensure the participant is comfortable. If any side effects occur that are rated by the participant as stronger than "moderate", or the participant reports severe discomfort during stimulation, the stimulation session will be terminated immediately.

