7 STUDY INTERVENTION DISCONTINUATION AND PARTICIPANT DISCONTINUATION/WITHDRAWAL

7.1 DISCONTINUATION OF STUDY INTERVENTION

Discontinuation from stimulation does not mean discontinuation from the study, and remaining study procedures should be completed as indicated by the study protocol. If a clinically significant finding is identified (including, but not limited to changes from baseline) after enrollment, the investigator or qualified designee will determine if any change in participant management is needed. Any new clinically relevant finding will be reported as an adverse event (AE).

The data to be collected at the time of study intervention discontinuation will include the following:

- All remaining study questionnaires

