8.2 SAFETY AND OTHER ASSESSMENTS

Pre-screening for the study will involve review of the medical chart for the presence of exclusionary criteria, particularly medical conditions and medications, which may put the participant at risk during the study. These criteria will also be reviewed with the participant at the screening visit and at each stimulation session prior to stimulation. Screening will be performed within 21 days of initial study stimulation visit.

Safety will be monitored throughout the study. A stimulation adverse effects questionnaire will be used based on common side effects experienced with TMS. This questionnaire will be administered at the end of each stimulation session. Additionally, participants will be continually asked about their comfort level during stimulation sessions. If a participant reports greater than moderate level of discomfort during stimulation, the stimulation will be immediately discontinued.

The PI will monitor the study for any adverse and serious adverse events. All serious adverse events will be reported to the IRB. Should there be a serious adverse event that occurs that increases the risks to the participants, the study will be stopped and an investigation will be conducted and a findings report generated before the study is resumed. At the time of enrollment, we will ensure we have an active and accurate phone number on file to contact the subject.

Medical follow-up

In the event that a subject is found during the course of the study to need medical or psychological follow-up related to their study involvement, the following procedures will be followed to address their issues.

Medical: For urgent issues, we will direct subjects to the nearest emergency room versus urgent care center for evaluation, based off of the described difficulties and symptoms. For nonurgent (subacute, chronic) issues related to neurologic condition, a follow-up appointment within our department will be scheduled for within 72 hours of the communication. If the issue is unrelated to their movement disorder but also nonurgent, we will communicate with the subject's primary care physician and, when appropriate, disclose necessary information regarding the study protocol should it be relevant to the complaints at hand.

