9.3 POPULATIONS FOR ANALYSES

We will use a modified Intention-to-Treat Analysis Dataset (e.g. participants who at least started the stimulation, whether or not they were able to complete the stimulation session, and/or sufficient follow-up outcome data).

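### The safety tables cover adverse events that end study participation and serious events, but no planned output counts sessions stopped early for intolerance in participants who stay in

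*Combined protocol and SAP*

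**What the plan says.** All places are in the combined protocol and SAP.

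- **Safety tables (9.4.4).** Two categories of adverse event are assigned to a table: "Adverse events leading to premature discontinuation from the study, and serious treatment-emergent AEs, will be presented in a table".
- **Other safety reporting (9.4.4).** The adverse effects questionnaire completed after each session is summarised by mean, median and range. For adverse events generally, "AEs will be reported as start date, stop date, severity, relationship to stimulation, expectedness, outcome, and duration". The counting rule is "Each AE will be counted only once per participant".
- **Intolerance rule.** Section 2.3.1 says that when a side effect is rated above moderate, or discomfort is severe, "the stimulation session will be terminated immediately". Section 8.2 says: "If a participant reports greater than moderate level of discomfort during stimulation, the stimulation will be immediately discontinued".
- **Status after stopping (7.1).** "Discontinuation from stimulation does not mean discontinuation from the study, and remaining study procedures should be completed as indicated by the study protocol".
- **Analysis set (9.3).** The modified intention-to-treat set keeps participants who started stimulation, "whether or not they were able to complete the stimulation session".
- **What is recorded (8.3.5).** The adverse event log includes a field for the action taken.
- **Listings (9.4.8).** Individual participant data are not to be listed.

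**The concern.** The discontinuation table is keyed to leaving the study, whereas the protocol's stated response to intolerance is to stop the session. Since 7.1 separates the two, the table can miss the tolerability event that the protocol itself defines.

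This matters for two reasons. Section 2.1 gives the overarching objective as the feasibility of using TMS for autonomic dysfunction and depression in Parkinson's disease, and how often stimulation had to be stopped, and at which site, is basic information for that question. Secondly, because 9.3 retains incomplete sessions, some Aim 1 post-stimulation EEGs may follow a partial session, and no count of these is planned.

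**Working it through.** The plan states no figure on this point, so there is none to reproduce. The check is a comparison of the text, followed by arithmetic for scale.

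**Step 1. Follow one case through the outputs.** Take a non-serious side effect that stops a session in a participant who then continues.

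| Planned output | Does it show that the session was stopped? |
|---|---|
| Table of events leading to study discontinuation (9.4.4) | No. The participant has not left the study (7.1). |
| Table of serious treatment-emergent events (9.4.4) | No. The event is not serious. |
| Reporting of event attributes (9.4.4) | No. The event appears with severity, relationship and outcome, but the action taken is not among the reported items. |
| Questionnaire mean, median and range (9.4.4) | No. A high rating may appear as the maximum, but that is not a count of stopped sessions. |
| Individual listings (9.4.8) | None are planned. |
| Compliance (6.3) | Defined as completing all three sessions, but 9.4 plans no tabulation of it. |

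The log in 8.3.5 can hold the information, but no output in 9.4 draws on that field.

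**Step 2. Site.** Each participant is stimulated at three sites, one per session. Section 9.4.4 states no breakdown by site and counts each adverse event once per participant. The same intolerance at two sites could therefore be reduced to one event.

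**Step 3. Two other routes.** A participant withdrawn for an adverse event at the investigator's discretion (7.2, 10.1.7) does enter the discontinuation table. A serious event enters the other table. The gap is confined to non-serious events in participants who stay in.

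**Step 4. Scale.** Inputs: 48 participants (6.2) and 3 sessions each (1.1). Planned sessions: 48 × 3 = 144, or 48 per site. The stop rate per session, p, is an assumption. Expected stopped sessions = n × p. Probability of at least one, treating sessions as independent, = 1 − (1 − p)^n.

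| Assumed p | Expected per site (n = 48) | P(at least one) per site | Expected overall (n = 144) | P(at least one) overall |
|---|---|---|---|---|
| 1% | 0.48 | 0.383 | 1.44 | 0.765 |
| 2% | 0.96 | 0.621 | 2.88 | 0.945 |
| 5% | 2.40 | 0.915 | 7.20 | 0.999 |
| 10% | 4.80 | 0.994 | 14.40 | above 0.999 |

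Independence is reasonable within a site, where each participant contributes one session. It is only approximate across all 144, since three sessions come from each person.

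**The case against.** The strongest reply is that little is hidden. An event that stops a session exceeds moderate by the rule's own terms. Section 8.3.3.1 grades events as mild, moderate or severe, and 9.4.4 reports severity and relationship, so such an event should appear among the severe, stimulation-related ones. The questionnaire follows every session and its range is reported. Feasibility is rationale in 2.1, and section 3 lists no feasibility or tolerability outcome. No efficacy estimate or power figure is affected, and section 2.3.1 describes the commoner side effects as mild.

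Most of this stands, and it sets the limits of the point. A reader might infer that intolerable sessions leave no trace in the safety report. The documents do not support that, because the underlying event is still reported and serious events have their own table. A reader might also infer that the intolerance rule keeps people in the study. It does not say so: 7.1 means only that stopping stimulation is not automatically leaving, while 7.2 and 10.1.7 allow withdrawal for an adverse event.

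The reply does not supply the missing count. A participant's rating and a clinician's severity grade can differ, so severe related events are an imperfect proxy for stopped sessions. A maximum questionnaire score also says nothing about how many sessions ended early or where.

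**Conclusion.** The point holds in a limited form. For a non-serious event in a participant who stays in, the plan would report the symptom but not that it stopped the session, nor the site. No output in 9.4 counts stopped sessions.

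The size cannot be stated. The 1% to 10% range above is assumed, and the documents support neither a particular rate nor a claim that tolerability would be misstated by a given amount. Nor would a report of no study discontinuations be false; it would answer a different question from how many sessions were stopped.

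The conclusion rests on reading the items in 9.4.4 as the full set of planned safety outputs. It is a worthwhile, inexpensive reporting improvement that serves the objective in 2.1, and it does not challenge any efficacy analysis.

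**What to change.** In 9.4.4, replace the single study-discontinuation category with three, tabulated separately, and keep the table of serious events. The three are adverse events leading to:

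- (a) early termination of a stimulation session;
- (b) no further stimulation sessions;
- (c) withdrawal from the study.

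Give (a) by stimulation site, with sessions started at that site as the denominator, using the action-taken field of the adverse event log. State that (a) is counted per session, so that the once-per-participant rule does not merge events at different sites.

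Also report the number of iTBS sequences delivered per session, if session records capture it. The documents do not say that they do, so the sponsor should confirm. Section 4.3 allows up to four repeats of the sequence, while 6.1.2, 6.1.3 and 8.1.2 state four. Those passages must be reconciled before a lower count can be read as a partial session, and even then a lower count alone would not show intolerance.

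The cost is a short edit to 9.4.4 and one extra table, with the small downside that the tolerability summary may look less favourable. No stopping rule or stimulation parameter changes.
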